This population and their social vulnerabilities also place them at disproportionate risk for COVID-19 acquisition, morbidity, and mortality.¹¹⁷⁻¹¹⁸ Many social vulnerabilities¹¹⁹ also increase risk of negative COVID-19 outcomes, including poverty, homelessness, and residence in congregate and transitional group homes, emergency shelters, and long-term care facilities where viral transmission has happened rapidly. Without specific training on COVID-19, these vulnerabilities will continue to be a source of unchecked community transmission that will have larger societal impacts.

We received funding to develop and evaluate the effectiveness of a 3-session I-IMR module to provide specific training on how to prevent contracting and spreading COVID-19 and other acute viral infectious diseases that may arise in the future and will similarly require: 1) knowledge and enactment of measures to maximize personal and societal safety (e.g., safely acquiring food, paying bills, accessing healthcare and COVID-related resources), 2) use of illness self-management behaviors to reduce risk of contracting and spreading illness, and 3) methods for addressing social determinants of health (e.g., maintaining social connection while ensuring physical distancing).

This component of the project will involve: 1) an initial needs assessment that will inform the refinement and specification of the training materials in the 3-session I-IMR COVID-19 and viral infectious disease module, 2) delivery of the module in phone or video-based sessions with a clinician trained in I-IMR, and 3) evaluation of the impact of the module on key outcomes. I-IMR participants will receive this 3-session module, which will be individually-delivered by phone or video (e.g., secure Zoom) to 75 participants (current and future participants assigned to I-IMR). We are not at liberty to add training on infectious viral diseases to CDSMP because this is not our intervention. The CDSMP participants are essential to the study as they serve as the comparison group, preserving the comparative effectiveness design, as required by PCORI.

2. Objectives and Hypotheses

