The proposed study will randomize people with serious mental illness to I-IMR (n=300) and CDSMP (n=300) to address the following four specific aims and hypotheses:

Aim 1: Compare the effectiveness of I-IMR to CDSMP with respect to our primary ***physical health self-management outcomes***.

Hypothesis 1: I-IMR compared to CDSMP will be associated with greater improvements in ***physical health self-management abilities*** (Self-Rated Abilities for Health Practices scale; SRAHP, and a qualitative interview) and ***physical health consumer activation*** (Patient Activation Measure; PAM); and (secondary hypothesis) greater improvement in self-reported ***physical health*** functioning (PROMIS Global Health measure).

Aim 2: Compare the effectiveness of I-IMR to CDSMP with respect to our primary ***mental health self-management outcomes***.

Hypothesis 2: I-IMR compared to CDSMP will be associated with greater improvements in ***mental health self-management abilities*** (Illness Management and Recovery Scale; IMRS, and a qualitative interview); and ***mental health consumer activation*** (PAM-MH); and (secondary hypothesis) greater improvement in self-reported ***mental health*** (PROMIS Global Health measure).

Aim 3: Compare the effectiveness of I-IMR to CDSMP with respect to ***emergency room and acute care hospital days***, and risk of ***10-year cardiovascular mortality***.

Hypothesis 3: Participation in I-IMR compared to CDSMP will be associated with fewer emergency room admissions and acute care hospital days over 12 months compared to the 12 months before participation; and greater reduction in 10-year cardiovascular risk score (ACC/AHA Cardiovascular Risk Score) from baseline to 12 months.

Aim 4: Compare I-IMR to CDSMP with respect to subgroup differences in self-management outcomes by **mental illness subgroup** (schizophrenia-spectrum vs. mood disorders) and by **age group** (18-49 vs. 50+).

Hypothesis 4: Comparing I-IMR and CDSMP, the difference in treatment effects will be greater for people with schizophrenia spectrum disorders compared to mood disorders; and greater for older (age 50+) compared to younger (18-49) participants with respect to: **physical health self-management abilities and activation** (SRAHP; PAM); **mental health self-management abilities and activation** (IMRS; PAM-MH); and 10-year ***cardiovascular risk reduction*** (ACC/AHA Cardiovascular Risk Score).

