COVID-19 Enhancement Primary Aim: After co-design of the 3-session I-IMR module, we will evaluate the impact of the module by comparing participants assigned to I-IMR (n=75) to participants assigned to CDSMP (n=75) on the primary and secondary outcomes (**primary**: knowledge and use of measures to prevent contracting and spreading COVID-19; **secondary**: use of healthcare services for COVID-related concerns; perceived isolation and social disconnectedness).

Primary Hypothesis: I-IMR participants will demonstrate greater improvements in their scores on the primary outcome measure (a measure of knowledge and behaviors to prevent contracting and spreading COVID-19 developed for this project) compared to CDSMP participants.

Secondary Hypothesis: I-IMR compared to CDSMP participants will demonstrate less COVID-related health care service use and greater improvements in social connectedness.

Exploratory Aim: Explore differential response with respect to race/ethnicity (Black versus White adults); age (older versus younger adults); and psychiatric diagnosis (schizophrenia-spectrum vs. mood disorders).

Exploratory Hypothesis: Effect sizes for the I-IMR module versus generic support calls alone will be even greater among Blacks v. Whites, older (55+) v. younger adults, and people with schizophrenia-spectrum v. mood disorders.

3. Study Design

The proposed study is to compare I-IMR and CDSMP in improving outcomes of importance to the target population of people with SMI: optimizing personal physical and mental health, being an active agent in determining personal physical and mental health wellness goals, decreasing risk of early mortality, and minimizing use of the ER and hospitals. A secondary objective is to learn whether psychiatric diagnosis and/or age interacts with treatment, specifically, whether treatment effects vary more for participants with schizophrenia or older age. Consistent with a truly pragmatic trial, inclusion criteria are broad and exclusion criteria are limited. Participants will be randomized, stratified by diagnosis (schizophrenia spectrum vs. mood disorder) and age group (age 18-49 vs. age 50+).

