The Needs Assessment required as part of the COVID-related component of the project involves qualitative interviews by research staff with 10 clinical staff who work directly with clients, and 20 participants who have already enrolled in I'M Well. The Site Coordinators and Site PIs at each site will meet to select staff who work most closely with service users and therefore are in the best position to comment on how they are handling the COVID-19 pandemic and what they need at this time. The Site Coordinators will identify participants for the needs assessment, which will be conducted by members of the PI's research team (including review of an information sheet describing the interview and process), and will coordinate the appointments and arrange for them to be audiotaped to permit evaluation of themes. We could have used an approach in which each person would have an equal chance to participate using randomly generated numbers. However, this could have resulted in an imbalanced group (for example, mostly white males). We felt it was essential to hear a wide range of perspectives, from participants who reflect the characteristics of the broader study population. For example, we wanted to be sure to include equal numbers of males and females, equal numbers of CDSMP and I-IMR participants, participants from a diverse set of racial and ethnic backgrounds, older and younger people. Therefore, the Study Coordinators will work to ensure that the individuals who will be invited are a diverse group. Site Coordinators will also provide the compensation for the interviews (\$50 VISA card for participants, \$25 restaurant gift card for staff).

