These interviews will inform development of the curriculum for the 3-session I-IMR module on COVID-19 and other viral diseases. This component of the project will also involve development of the primary outcome measure, given that no appropriate measure of COVID-19 knowledge and use of behaviors to avoid catching and spreading disease was available. After finalizing the curriculum for the 3-session I-IMR module, interventionists will be trained to deliver it by phone or video. We will record the sessions to permit supervision and fidelity assessment by the co-developers of I-IMR. All participants have already consented to audiotaping or videotaping of IIMR sessions. Research staff will conduct baseline, 6- and 12-week assessments by phone with all participants (75 I-IMR and 75 CDSMP participants). (Site Coordinators will first complete informed consent to participate in this project, by phone using the procedure described below). We will work with the statisticians from the I'M Well project to complete data analyses.

Site Coordinators will contact individuals who have been randomized to I-IMR and CDSMP to invite them to participate in this component of the project. I-IMR group participants will be offered the 3 session I-IMR module and asked to participate in a phone-based assessment no more than one week prior to receiving the intervention (baseline), a second assessment no more than two weeks after completing the 3 sessions (6 week assessment), and a third assessment approximately 12 weeks after receiving the last session of the module (12 week assessment). CDSMP group participants are receiving usual care, which includes generic supportive telephone calls from agency staff. They will be asked to participate in phone-based assessments on the same schedule as the I-IMR participants. For both groups (I-IMR & CDSMP), Site Coordinators will call participants to review a description of the project in the consent form. Consent to participate will be obtained by phone.

Interventions to be Compared

IIMR (Integrated Illness Management and Recovery vs. CDSMP (Stanford Chronic Disease Self-Management Program)

Overview of Integrated Illness Management and Recovery (I-IMR): I-IMR combines 4 evidence-based psychosocial interventions for SMI: (1) *psychoeducation*, which improves knowledge about

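### The COVID component states no rule for whom coordinators invite although they must know the arm, so the two sets of 75 need not be comparable

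*Combined protocol and SAP*

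**What the plan says.** The main trial plans 300 participants per arm (Section 2, Objectives and Hypotheses). The COVID component takes 75 from each arm (Section 2, COVID-19 Enhancement Primary Aim), which is 150 of 600 (Section 9, item a).

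On recruitment, the COVID paragraphs of Section 3 (Study Design) say: "Site Coordinators will contact individuals who have been randomized to I-IMR and CDSMP to invite them to participate in this component of the project". The offer then differs by arm. "I-IMR group participants will be offered the 3 session I-IMR module", whereas CDSMP participants continue with usual care, including supportive calls from agency staff, and are asked only for assessments on the same schedule. The coordinators explain the component and take consent by telephone.

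The background text before Section 2 describes the I-IMR recipients as "75 participants (current and future participants assigned to I-IMR". No corresponding description, by stage of the main trial, is given for the CDSMP 75. The same text says that the CDSMP participants are there to preserve the comparative effectiveness design.

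Section 4 (COVID Component Analyses) fits group, time (baseline, 6 and 12 weeks) and their interaction. A significant interaction is taken to show that I-IMR is superior. The PHQ-9, GAD-7 and Fear of COVID Scale are named as potential covariates.

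**The concern.** Randomisation made the two full arms comparable. It does not make two subsets comparable if they are formed later by people who know the arm, under no stated rule. If those invited in one arm are more engaged, easier to reach or at a different stage of the main trial than those invited in the other, their scores could change differently even if the module did nothing.

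The planned analysis only partly guards against this. Measuring baseline and testing group by time removes a stable difference in level. It does not remove selection of people who are likely to change more, or less, over the next 12 weeks. The three potential covariates cover depression, anxiety and fear of COVID, not engagement or time since randomisation. The balance check and propensity weighting in Section 4 are written for the Aim 3 service-use analysis only. Nothing compares the two sets of 75 with each other, or entrants with non-entrants.

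At stake is whether a positive result can be credited to the module, and whether a null result can be believed.

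**Working it through.** **1. How the subset is formed.**
- Share of the planned arm: 75/300 = 25%. The number actually reachable while the component recruits is not given, so 25% is the lower limit of the share taken. If the reachable pool were close to 75, there would be little room for selection.
- Arm known at invitation: inferred, not stated. The offer is arm-specific, and for the needs assessment the coordinators were to obtain "equal numbers of CDSMP and I-IMR participants".
- Order of invitation, list, stratification, time window, refusal log: none stated.

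**2. The plan's own precision.** Section 4 (Power analysis) gives 75 per arm, 10% attrition, two-sided alpha 0.05 and 80% power at an effect size of 0.46 (taken here as SD units).
- Detectable effect = (1.960 + 0.842) × √(2/n) = 2.802 × √(2/n).
- n = 75: 2.802 × 0.1633 = 0.457, which matches 0.46.
- n = 67.5 (10% attrition): 2.802 × 0.1721 = 0.482.

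On this formula the stated figure appears only if attrition is left out. That is a separate matter, so both standard errors are carried forward: 0.46/2.802 = 0.164 and 0.482/2.802 = 0.172.

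**3. What a selection bias would do.** The documents give no figure for it, so the following are assumptions. Suppose that those invited in one arm exceed those in the other by g SD on some trait (engagement, say) that correlates r with gain. The bias in the contrast is b = g × r, with the SD of gain taken as the unit of the effect size. The two-sided false-positive rate is Φ(−1.96 + b/SE) + Φ(−1.96 − b/SE).

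| g | r | b (SD) | False-positive rate, SE 0.164 | False-positive rate, SE 0.172 |
|---|---|---|---|---|
| 0.2 | 0.1 | 0.02 | 5.2% | 5.2% |
| 0.4 | 0.3 | 0.12 | 11.3% | 10.7% |
| 0.8 | 0.3 | 0.24 | 30.9% | 28.6% |

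Worked for the middle row: 0.12/0.164 = 0.73, and Φ(−1.23) + Φ(−2.69) = 0.109 + 0.004 = 0.113. A gap of 0.8 SD is what arises if only the upper half of one arm on a normally distributed trait is invited while the other arm is representative (mean of the upper half = 0.80 SD). It is an extreme case.

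**4. The opposite direction.** If the bias runs against the module, power at a true effect of 0.46 is Φ((0.46 − b)/0.164 − 1.96). It falls from 0.80 to 0.59 at b = 0.10 and to 0.35 at b = 0.20.

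**5. No selection difference.** If the same selection acts in both arms, g is near 0 and so is the bias. With random or consecutive invitation and equal refusal the expected bias is zero, and the false-positive rate stays at 5%.

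**The case against.** The strongest reply is that the plan is silent, not wrong. Inviting everyone available, or inviting in order of entry, fits the recruitment sentence as well as any other practice, and the mention of current and future participants is compatible with rolling enrolment. This stands, and it rules out three stronger readings that a reader might infer.

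- *That coordinators pick participants at their own discretion.* The documents do not say so. What can be said is that no rule or order is stated.
- *That random selection was rejected for this comparison.* Section 3 does say "We could have used an approach in which each person would have an equal chance to participate using randomly generated numbers", but that sentence concerns the 20 participants interviewed for the needs assessment, where seeking a diverse group is reasonable. It is not the rule for the 75 and 75.
- *That the I-IMR invitees will mostly be people still attending while CDSMP people have finished.* I-IMR has 16 sessions and CDSMP runs for 6 weeks, but nothing shows how many people were in either programme at the time. Invitation is by telephone and the module is delivered individually by phone or video, so nothing ties invitation to group attendance.

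It is also fair to say that the bias sizes are assumed, that the direction is not known (engaged people might start higher on a knowledge measure and gain less), and that the covariates in the plan may absorb some of a difference.

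This limits the claim about size and mechanism but leaves the gap open. A superiority test on a subset recruited with the arm known needs a stated rule, even if nobody misuses its absence. If the intention is to invite everyone or to go consecutively, one sentence would settle the main part of the point.

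**Conclusion.** The concern holds as a gap in the design of the COVID component. The plan gives no invitation rule for two post-randomisation subsets recruited with the arm evidently known, no matching definition of the two pools and no check of comparability, yet it reads the interaction as superiority. It should be corrected, but it concerns the add-on only; the main comparisons in Aims 1-4 are unaffected.

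How large the effect would be cannot be determined from the documents. Under the assumed range it runs from negligible (0.02 SD) to serious (0.24 SD, false-positive rate about 31%). The upper end needs strong selection in one arm only, which nothing in the documents suggests has happened or will happen. Knowledge of the arm is an inference from the arm-specific offer, though a secure one.

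**What to change.** State the invitation rule in Section 3 and the matching checks in Section 4.

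1. For each site, the study statistician supplies a randomly ordered call list within each arm. Inviting all eligible people, or inviting consecutively by randomisation date, would also do.
2. Use the same eligibility window by time since randomisation in both arms, and add newly randomised people as they enter, so that future participants are covered.
3. Coordinators work the two arms' lists in parallel over the same weeks. They log by arm who was invited, not reached, refused and consented.
4. Compare the two sets of 75 on main-trial baseline data and time since randomisation.
5. Prespecify adjustment for time since randomisation, the diagnosis and age strata, and site. This is needed because people know what their arm is offered when they decide, so refusal can differ by arm even with a random list.

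The list should be simple. Crossing arm with diagnosis, age and bands of time at each site would leave only a few people per cell; adjustment deals with those factors more practically.

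The sample size, module and outcomes stay the same. The cost is a list per arm at each site, a call log and perhaps slightly slower recruitment, because coordinators must try people in list order. Steps 1 to 3 work only for invitations not yet made; steps 4 and 5 can be added at any time before the analysis.

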Overview of the Stanford Chronic Disease Self-Management Program (CDSMP): CDSMP is a 6-session group-based educational program co-delivered by two peers (lay people who have successfully managed a chronic illness) or a peer and a medical professional.^{21,22} This 6-week program covers techniques for dealing with problems such as: frustration, fatigue, pain and isolation; appropriate exercise for maintaining and improving strength, flexibility and endurance; appropriate use of medications; communicating effectively with family, friends and health professionals; nutrition; and evaluating new treatments (see Table 2). A meta-analysis of 23 studies of the CDSMP program *in general populations* conducted by the Centers for Disease Control and Prevention in 2013 found 4-6

| | | |
|--|---------------------------------------|---|
| -Identifying Common Problems | -Problem Solving | -Making Informed Treatment Decisions |
| -Differences between Acute and Chronic Illnesses | -Better Breathing | -Depression Management |
| -Using Your Mind to Manage Symptoms | -Pain and Fatigue Management | -Positive Thinking |
| -Making an Action Plan | -Endurance Activities | -Guided Imagery |
| -Dealing with Difficult Emotions | -Future Plans for Health Care | -Working with Your Health Care Professional |
| -Intro to Physical Activity and Exercise | -Healthy Eating Communications Skills | -Looking Back and Planning for the Future |
| | -Medication Usage | |

month improvements in energy, fatigue, self-rated health, aerobic exercise, cognitive symptom management, psychological health, communication with physicians, and health care utilization.⁶² CDSMP is currently offered in over 45 states and over 19 countries.

Table 2: The Stanford Chronic Disease Self-Management (CDSMP) Curriculum

4. Analysis

Evaluation of Group Equivalence.

Subgroup analysis for treatment effects (i.e., estimate of the treatment effect for each subgroup) is a common approach for HTE analysis. However, this approach is susceptible to the issue of multiple post hoc analyses. We have a total of 20 subgroup analyses (5 outcome measures by 4 subgroups), thus we will adjust the p-value to account for multiple tests for each subgroup analysis and use the false discovery rate method⁹⁰ implemented in SAS software.⁹¹ Subgroup analysis may increase the

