likelihood of Type II error due to small sample sizes. Therefore, we will not rely on statistical tests and p-values alone to evaluate HTE; we will rely on estimated effect sizes (estimate divided by the standard deviation) and compute confidence intervals around these effect sizes.

Evaluation of Attrition

We will recruit 600 participants and randomly assign them to two arms with equal allocation (300 per arm). Based on previous experience, we assumed 20% attrition by 12 months. In addition to enhancing the process of full informed consent, these procedures are designed to decrease the likelihood of study attrition due to inadequate appreciation of the time, effort, and component activities involved in participating in the intervention program, or in the study protocol.

Analyses for Primary Study Aims and Hypotheses

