Analysis for Aim 4: In **Aim 4**, we compare I-IMR to CDSMP with respect to subgroup differences in self-management outcomes by ***mental illness subgroup*** (schizophrenia-spectrum vs. mood disorders) and by ***age*** (18-49 vs. 50+) based on our belief that greater cognitive limitations and comorbid health conditions may require more intensive and specialized self-management training consistent with I-IMR. We hypothesize that when comparing I-IMR and CDSMP, the difference in treatment effects will be greater for schizophrenia spectrum disorders compared to mood disorders; and greater for older (age 50+) compared to younger (age 18-49) participants with respect to: ***physical health self-management abilities and activation; mental health self-management abilities and activation*** and 10-year ***cardiovascular mortality risk reduction***. In this aim, we examine heterogeneity of treatment effects (HTE) using subgroup analyses. Because we pre-specified the 2 subgroups (diagnosis and age) and hypothesized the differential treatment effect between subgroups based on the literature, our approach is confirmatory (hypothesis driven) HTE analysis. To test HTE, we will use the same analytic models, GLMM for **Aim 1**, **Aim 2** and **Aim 3**, but we will include 3-way interaction terms (arm*time*group) in each model. A significant 3-way interaction effect will indicate the existence of the heterogeneity of treatment effects between subgroups. Following this step, we will conduct simple effect analysis to estimate treatment effect differences (a difference in slopes by time effect between arms) within each subgroup. Although our HTE analysis is hypothesis driven, we will report p-values for hypothesis testing for all subgroup analyses. We will also evaluate HTE by examining the magnitude of treatment effects with standard errors (clinically meaningful effect sizes) as outlined in PCORI Methodology Standards⁸⁸ and recommended by statisticians.⁸⁹

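### Aim 4 does not say whether the interaction contrast or the within-subgroup effect sizes decide heterogeneity, and its stated FDR family is the 20 within-subgroup effects, not the 10 contrasts being tested

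*Combined protocol and SAP*

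**What the plan says.** Hypothesis 4 (Section 2) concerns a difference between subgroups. The advantage of I-IMR over CDSMP is expected to be larger in schizophrenia-spectrum than in mood disorders, and larger at 50 and over than at 18-49, on five outcomes (SRAHP, PAM, IMRS, PAM-MH and cardiovascular risk).

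The Aim 4 paragraph of Section 4 calls this analysis confirmatory, adds a three-way term to each model and states: "A significant 3-way interaction effect will indicate the existence of the heterogeneity of treatment effects between subgroups". Simple effects within each subgroup come next, described as "a difference in slopes by time effect between arms". They are not made conditional on a significant interaction. The same paragraph says that heterogeneity will additionally be assessed from the size of treatment effects with their standard errors.

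The subgroup text under Evaluation of Group Equivalence (also Section 4) uses a different unit of analysis. It begins: "Subgroup analysis for treatment effects (i.e., estimate of the treatment effect for each subgroup) is a common approach for HTE analysis". It counts the tests so: "We have a total of 20 subgroup analyses (5 outcome measures by 4 subgroups". It then promises that "we will adjust the p-value to account for multiple tests for each subgroup analysis and use the false discovery rate method". Citing Type II error in small subgroups, it adds that tests and p-values will not be the only basis for judging heterogeneity, and that "we will rely on estimated effect sizes (estimate divided by the standard deviation) and compute confidence intervals around these effect sizes".

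The plan gives no confidence level, interval adjustment or effect-size threshold. It does not say which standard deviation is the divisor, or which evidence prevails if tests and effect sizes point different ways.

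**The concern.** The question and the error control are attached to different quantities. Hypothesis 4 is answered by between-subgroup contrasts. The FDR is promised for within-subgroup effects, and nothing extends it to the interaction tests. No interval is promised for the between-subgroup difference either.

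The stated reason for bringing in effect sizes is Type II error. They are therefore meant to carry weight when the tests are not significant, which is where an FDR on p-values gives no protection. One subgroup interval that excludes zero beside another that does not, or two point estimates some distance apart, is easily read as heterogeneity. Either pattern is common when the true effect is the same in both subgroups.

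At stake is a confirmatory statement that I-IMR works better for people with schizophrenia-spectrum disorders or for older participants, resting on differences that chance would produce. The primary comparisons of Aims 1 and 2 are not affected.

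**Working it through.** **Inputs from the documents.** Five Aim 4 outcomes; two factors with two levels each; 600 participants, 1:1; 20% loss by 12 months.

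**Assumed, not in the documents.** Equal subgroup split (others shown); 95% intervals; outcomes in SD units; a simple cross-sectional comparison of completers in place of the planned mixed model; the gap and common-effect sizes below. Two-sided 0.05 is stated only for the COVID component and is borrowed here.

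**1. Counts.** The plan's figure reproduces: 5 x 4 = 20 within-subgroup effects. The contrasts that answer Hypothesis 4 number 5 x 2 = 10. Completers: 600 x 0.80 = 480, or 240 per subgroup.

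**2. Standard errors.** A two-arm difference in a subgroup of size n has SE = sqrt(4/n). For n = 240 this is sqrt(4/240) = 0.129 SD. The difference between two such effects has SE = sqrt(4/240 + 4/240) = 0.183 SD, so its 95% interval is about plus or minus 1.96 x 0.183 = 0.36 SD. The two within-subgroup intervals do not show that width.

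**3. Chance gaps in point estimates, no heterogeneity.** P(gap of at least 0.2 SD in the predicted direction) = P(Z > 0.2/0.183) = 0.137, which is about 10 x 0.137 = 1.4 of the ten contrasts on average.

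| Split | SE of difference | Predicted direction, at least 0.2 SD | Either direction, at least 0.2 SD | Either direction, at least 0.3 SD |
|---|---|---|---|---|
| 50:50 | 0.183 | 0.137 | 0.27 | 0.10 |
| 35:65 | 0.191 | 0.148 | 0.30 | 0.12 |
| 25:75 | 0.211 | 0.171 | 0.34 | 0.155 |

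**4. One interval excludes zero and the other does not, same true effect.** With a common effect of 0.25 SD, power in each subgroup is P(Z > 1.96 - 0.25/0.129) = 0.49. The chance of exactly one exclusion is 2 x 0.49 x 0.51 = 0.50. With a 35:65 split it is 0.53. With a common effect of 0.2 SD it is about 0.45, and with no effect 2 x 0.05 x 0.95 = 0.095.

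**5. Where the FDR is applied matters.** Simulation: 3,000 trials per setting, 480 completers, five outcomes with mutual correlation 0, 0.3 or 0.6, two independent 50:50 factors, no heterogeneity, common effect 0 or 0.2 SD, Benjamini-Hochberg at 0.05. Each range spans the correlations and, unless the row names the effect, both effects.

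| Basis for a heterogeneity claim | Chance of at least one false claim |
|---|---|
| 10 interactions, no correction | 0.29 to 0.41 (1 - 0.95^10 = 0.40 if independent) |
| 10 interactions, FDR on those 10 | 0.036 to 0.056 |
| FDR on the 20 within-subgroup p-values, then contrasting significant with non-significant subgroups; common effect 0 | 0.04 to 0.05 |
| The same, common effect 0.2 SD | 0.53 to 0.74 |

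The planned FDR family controls false claims of an effect within a subgroup. It does not control false claims that subgroups differ once a common effect exists.

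**The case against.** The strongest reply is that the plan already has a formal criterion. The three-way interaction is said to indicate heterogeneity, simple effects come after it, and effect sizes are to be used as well as tests, not in their place. Effect sizes with intervals beside p-values are ordinary good reporting. No threshold and no rule about intervals excluding zero appears, so the rates in steps 3 to 5 for gaps and discordant intervals come from reading rules that the plan does not state. The standard errors are cross-sectional, whereas the plan fits repeated-measures models to the full sample. The study design section treats differences by diagnosis and age as a secondary objective.

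Much of this stands. The interaction test remains in the plan, effect sizes supplement it, and the figures are illustrative. What the reply does not supply is a precedence rule, an FDR on the ten interactions, or an interval for the quantity in Hypothesis 4.

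Some stronger readings go too far:

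- A reader might infer that the plan abandons error control, or that its intervals are definitely uncorrected. The text is silent on adjustment, which is not the same thing. It is also not explicit that the effect sizes are only within-subgroup ones, although the definition that opens the subgroup text makes that the natural reading.
- A reader might infer that dividing a slope by a standard deviation creates false heterogeneity because the result depends on the time unit. Changing the unit rescales both subgroups alike and alters no p-value and no relative comparison. It is a reporting ambiguity only.
- A reader might extend the point to the COVID component, where it is hypothesised that "Effect sizes for the I-IMR module versus generic support calls alone will be even greater among Blacks v. Whites". That hypothesis is labelled exploratory and comes with no subgroup decision method, so the argument about a confirmatory claim does not carry over.

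**Conclusion.** The point holds in limited form. For an aim called confirmatory, the plan names an interaction criterion, places its FDR on a different set of 20 quantities, and admits effect sizes and intervals as further evidence without a multiplicity rule or an order of precedence. Followed as written, it leaves room for chance gaps between subgroup effects to be reported as heterogeneity.

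Under the stated assumptions, such a gap of at least 0.2 SD in the predicted direction occurs in about 14% of contrasts (up to 17% with a 25:75 split). Discordant intervals occur about half the time at a common effect of 0.25 SD. The exact rates depend on the split, the effect sizes and the cross-sectional simplification. The direction does not: a between-subgroup difference is less precisely estimated than either within-subgroup effect, and a pair of within-subgroup intervals does not test it.

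This should be corrected before analysis. It does not touch the primary hypotheses of Aims 1 and 2.

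**What to change.** 1. State that the ten arm*time*group contrasts (5 outcomes by 2 factors) are the only confirmatory criterion for heterogeneity.
2. Apply the Benjamini-Hochberg FDR to those ten, and state the level. Making the contrasts decisive without this step would leave a 0.29 to 0.41 chance of at least one false finding in the simulated settings.
3. Report each between-subgroup difference in treatment effect with its confidence interval, whether or not the test is significant. This meets the Type II concern directly, because a wide interval shows what has not been ruled out.
4. Label within-subgroup effect sizes and intervals descriptive and not evidence of heterogeneity. Define them as the 12-month arm difference divided by one baseline SD from the whole sample, the same divisor in every subgroup.
5. If the beta model with logit link is used for cardiovascular risk, test the interaction on the model scale and report the risk-scale difference as descriptive.

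The cost is a few sentences in Section 4 and one reported contrast from each model already planned. The downside is that fewer subgroup statements can be made.
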